Facilitation approaches	Helpful phrases; Teaching skills; Medical and ACP topic discussion	Focus on story telling; emphasis on visual/written cues with simple language; encourage study partner to serve as “scribe” for goal-setting and ACP decisions
ACP resources	Folder of materials with goal-setting worksheet; Conversation Project; ¹² PREPARE website; ¹¹ advance directive forms	Go WISH visual cards (http://codaalliance.org/go-wish/) to facilitate values discussion; ¹⁴ easy-to-read advance directives ¹⁶
PCP integration	Documentation; PCP follow up	Facilitate PCP follow up for other aMCI needs; initiate social worker referrals
Clinic resources	Meeting space; Reminder calls; Staffing	Shorter meeting time (1.5 hour total); Sessions closer together (two weeks apart) or only one session

IV. Research Methods

A. Outcome Measure(s):

Aim 1: We have identified multiple potential outcomes for each key research questions. In line with qualitative research methods, we anticipate that new outcomes of interest will be identified during the analytic process for each of the study questions. Table 4, above, describes anticipated outcomes related to adaptations to the ENACT Group Visit intervention to meet the needs for individuals with aMCI.

Aim 2: We will evaluate feasibility of participation including recruitment and retention of patient-study partner dyads, participant acceptability, and feasibility of measuring patient- and caregiver-reported outcomes (as selected in Aim 1) for each n-of-1 ENACT Memory Group Visit intervention cycle.

Quantifiable outcome measures for the ENACT Memory Group Visit prototypes are summarized in **Table 5:**

Table 5. Pilot ENACT Memory Group Visit Outcomes		Data Sources

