2.3 Advance care planning outcomes		
Advance directive completion		Medical record
Self-efficacy, readiness for ACP		Patient survey
ACP discussions		Patient survey

Potential Modifiers of ACP Outcomes (Secondary Analysis): To identify aMCI participant characteristics that might influence feasibility and ACP outcomes, we will also examine the relationship between baseline cognitive function or mood symptoms (Table 6) and ACP outcomes. For example, we will examine whether better memory function or better executive functions are associated with advance directive completion. Cognitive, mood, and informant data from Bio-AD will be available for secondary analyses and will be referred to as their ‘baseline’ cognitive data. For participants who are not also participating in Bio-AD, we will a) offer participation in Bio-AD if they agree to participate in the recruitment data base, or b) not collect these baseline measures that are outlined in Table 6 due to the additional time requirements.

Table 6. Cognitive and Mood Measures Collected in [name] Study

	Primary Variable	Description
Cognitive		
Memory	SENAS: Memory Composite	Learning and delayed recall performance on a word list task.
Executive Functions	SENAS: Working Memory Composite	Verbal and visual working memory performance
	NACC Trail Making Test B (Total Time)	Cognitive flexibility and switching performance
Mood		
Depression	Geriatric Depression Scale (Total Score)	30-item questionnaire of current mood
Stress	Perceived Stress Scale (Total Score)	10-item questionnaire of recent perceived stress

We will collect qualitative data on implementation process measures, including interviews with patients and study partners, to understand the ACP-GV intervention from multiple perspectives.

B. Description of Population to be Enrolled:

Population and Setting:

Individuals with amnesic Mild Cognitive Impairment and study partners from UHealth settings: Memory Disorders Clinic, Seniors Clinics.

Aim 1 will recruit 6 older adults (\geq age 60) with aMCI and 6 associated study partners.

Aim 2 will recruit 20 older adults (\geq age 60) with aMCI and 20 associated study partners.

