Data Collection: All groups and interviews will be conducted at a convenient location for participants. A qualitative research assistant will create detailed field notes. All sessions (~1.5 hours each) will be audiotaped and transcribed. After each meeting, our multidisciplinary team will utilize iterative, inductive, and deductive analytical strategies including field notes and memos; qualitative content methods of analysis; and reflexive team analysis^{20, 21} of transcriptions to identify suggested ACP decision tools (**Q1a**), appropriate facilitator or structural design adaptations (**Q1b**), and meaningful patient and study partner/caregiver outcomes (**Q1c**). Detailed logs of analysis and interpretation, transcripts, and coding will be maintained to ensure transparency. ATLAS.ti will be used for data management.

Aim 2: Conduct a single arm feasibility study of the ACP-GV with suggested adaptations from aMCI patient-study partner dyads.

Research Methods: We will conduct four cycles of n-of-1 ACP-GV interventions involving up to five patient-study partner dyads per group (n=8-10 per cohort; n=32-40 total participants). Each cycle will use qualitative evaluations, human-centered design principles, and rapid prototyping to address the following ACP-GV intervention questions:

Question 2a: Is it feasible to recruit aMCI patient-partner dyads to the adapted ACP-GV and collect participant-reported meaningful outcomes (i.e., acceptability, appropriateness, beneficial or helpful)?

Question 2b: In the context of the ACP-GV intervention, what are mechanisms of action for ACP-related decision making in aMCI?

Intervention Development: The current ACP-GV intervention consists of up to 12 patients meeting in two 2-hour sessions, one month apart (see Appendix for ENACT Implementation Manual). In Aim 2, we will conduct four n-of-1 ACP-GV interventions with specific adaptations. To generate ideas for adaptations, we (researchers and patient-study partner stakeholders) will use rapid-prototyping methods guided by The Bootleg toolkit from the Institute of Design at Stanford.²² This free, online, state-of-the-art resource outlines a human-centered design process and describe dozens of specific methods to support design thinking work. Each n-of-1 ACP-GV intervention will be guided by detailed suggestions from the

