Aim 1: Qualitative Analysis Plan: Data analysis occurs longitudinally and begins at the time of the first focus group meeting as participants generate ideas and provide concrete suggestions for intervention adaptation. The words participants use, their beliefs, needs, and preferences will be described. The qualitative research analyst and I will initially code individually and then meet to discuss codes, establish inter-code reliability, and create an initial code list. The code list will be revisited and revised with each subsequent focus group meeting. Text within and between codes will be compared to develop themes. We will use observer triangulation (using the multidisciplinary team), participant triangulation (comparing patient and study partner perspectives) and member checking (eliciting feedback while returning results at the final meeting) to increase validity.

Aim 2: Analysis Plan: Data will be stored in a secure REDCap database.²³ For feasibility (**Q2a**), we will track recruitment and participation rates, including reasons for not participating. We will track the length of time to complete and completeness of participant-reported outcomes, as well as level of assistance provided by a research assistant (i.e. reading questions aloud; repeating questions; filling out responses). To address the question of mechanisms of action for ACP-related decision making (**Q2b**), each n-of-1 ACP-GV session will be audio

and video recorded, transcribed, observed by a research assistant who will create field notes, assessed for intervention fidelity to the planned adaptations, and formally de-briefed by the team to capture “what worked and what did not work?” Additionally, follow-up interviews will be conducted with more than half of participants after each session. The qualitative analysis will be conducted as outlined in Aim 1 to address feasibility, acceptability, and mechanisms of action for ACP-related decision making in aMCI.

Because this is a feasibility study that involves iterative development and refinement of the ENACT Memory Group Visit, a power calculation is not appropriate.

G. Summarize Knowledge to be Gained:

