**Study setting and population:** I will recruit 16 older adults ( $\geq$  age 65) affected by aMCI or early ADRD and 16 associated study partners from [name] existing research studies and other University of Colorado Hospital settings as described in Aim 1. The inclusion and exclusion criteria, recruitment process, and informed consent process are the same as for Aim 1, and are described in the Human Subjects form.

**Intervention Development:** The current ACP-GV intervention consists of up to 12 patients meeting in two 2-hour sessions, one month apart (**Table 1**). In this supplement Aim 2, we will conduct four n-of-1 ACP-GV interventions with planned adaptations. To generate ideas for adaptations, we (researchers and patient/study partner stakeholders) will use rapid-prototyping methods guided by The Bootleg toolkit from the Institute of Design at Stanford. This free, on-line, state-of-the-art resource outlines a human-centered design process and describe dozens of specific methods to support design thinking work. Each n-of-1 ACP-GV intervention will be guided by detailed suggestions from the aMCI/ADRD stakeholders, including potential changes to the Facilitator Guide and specific facilitation prompts and discussion topics, planned use of ACP decision tools, modified or new handouts, and specific resources to meet the needs of individuals with aMCI/ADRD. Each n-of-1 ACP-GV intervention will be approximately every two to three months, based on the evaluation, analysis, stakeholder focus groups, planning detailed changes to the next cycle, and recruitment of study participants.

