**Outcomes:** We will evaluate feasibility of participation including recruitment and retention of patient-study partner dyads, participant acceptability, and feasibility of measuring patient- and caregiver-reported outcomes (as selected in Supplement Aim 1) for each n-of-1 ACP-GV intervention cycle. We will also assess patient-level baseline and 3-month ACP outcomes using validated instruments from the parent K76 award (i.e., primary outcome: advance directive completion, secondary outcomes: self-efficacy, readiness, ACP discussions). To understand potential impact of the ACP-GV intervention on cognitive or mood-related outcomes, we will assess As with the parent K76 study, I will collect qualitative data on implementation process measures, including interviews with patients and study partners, to understand the ACP-GV intervention from multiple perspectives.

**Data Collection and Analysis:** Data will be stored in a secure REDCap database. For feasibility (**Q2a**), we will track recruitment and participation rates, including reasons for not participating. We will track the length of time and completeness of responses for the participant-reported outcomes, as well as level of assistance provided by a research assistant (i.e. reading questions aloud; repeating questions; filling out responses). To address the question of mechanisms of action for person-centered approaches to ACP-related decision making (**Q2b**), each n-of-1 ACP-GV intervention session will be audio and video recorded, transcribed, observed by a research assistant who will create field notes, assessed for intervention fidelity using the Fidelity Checklist with the planned adaptations, and formally de-briefed by the facilitator team to capture “what worked and what did not work.” Additionally, follow up interviews will be conducted with more than half of the participants (20 patients or study partners) after completing the session. The qualitative analysis will be conducted following the methods outlined in Supplement Aim 1 to address the questions of feasibility, participant acceptability, and mechanisms of action for ACP-related decision making in individuals with aMCI/ADRD.

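### Q2a tracks survey help only from a research assistant, so study-partner help would go unrecorded and patients' ability to self-report could be overstated

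*Protocol*

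**What the plan says.** Under Aim 2 of the Data Analysis Plan (Protocol IV.F), the burden of data collection for Q2a is measured in three ways. Two are given as "We will track the length of time to complete and completeness of participant-reported outcomes". The third is "level of assistance provided by a research assistant (i.e. reading questions aloud; repeating questions; filling out responses"). The SAP (Supplement Aim 2, Data Collection and Analysis) uses the same third item: "as well as level of assistance provided by a research assistant (i.e. reading questions aloud; repeating questions; filling out responses"). The question these items serve is whether it is feasible to "collect participant-reported meaningful outcomes (i.e., acceptability, appropriateness, beneficial or helpful").

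Every patient comes with a partner. Protocol IV.B plans 20 older adults "with aMCI and 20 associated study partners"; the SAP plans 16 people "affected by aMCI or early ADRD and 16 associated study partners". Table 4 in Protocol III lists, among possible adaptations, to "encourage study partner to serve as “scribe” for goal-setting and ACP decisions". Protocol IV.D has separate pre/post surveys for patients and partners and a telephone survey at 3 months. Neither document says whether the partner may be present or help while the patient answers.

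**The concern.** The plan already treats help with surveys as a feasibility outcome and names three kinds of it, but it counts help from one source only. The other likely helper is the study partner, whom the design recruits with every patient and whom the Protocol describes as being in frequent contact with the patient. If the partner reads the questions, prompts, or supplies answers, the record shows a form with no research-assistant help, possibly fully complete. That is also what a form completed alone looks like.

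Two things are at stake. First, the answer to Q2a could look better than it should, and the study is meant to inform a later pragmatic trial that must choose between self-report, assisted report and proxy report. Second, self-efficacy, readiness and ACP discussions come from the patient survey (Table 5), and the SAP names them as secondary outcomes. If some answers are the partner's, nothing marks them. Who helped cannot be reliably reconstructed once the data are in.

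**Working it through.** There is no planned figure to reproduce. The Protocol states that a power calculation is not appropriate, and neither document sets a target or threshold for assistance.

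**Step 1: could another planned item show partner help?**

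- Completeness and time to complete do not say who answered or who helped.
- Field notes, recordings and de-briefs are planned for the group sessions, not for survey completion.
- Follow-up interviews with more than half of participants might bring up partner help by chance. They are not described as asking about it, and they would not link it to a form.
- The partner's own survey does not record what the partner did on the patient's survey.

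So nothing described in the two documents separates partner-helped forms from unaided ones.

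**Step 2: how far could the picture shift?**

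Inputs:

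- *n*, patients with one survey each at a given time point: 20 (Protocol IV.B) or 16 (SAP, Study setting and population). The Protocol's Aim 2 range of 32 to 40 participants gives the same limits: 32/2 = 16 and 40/2 = 20 dyads.
- *a*, patients helped by a research assistant: not given.
- *p*, patients helped by the partner only: not given. The values 0, 1, 2, 5 and 8 below are assumptions.

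Formulas:

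- Share with no help recorded = (n − a)/n
- Share with no help at all = (n − a − p)/n
- Difference = p/n, so *a* cancels

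| p (assumed) | n = 20 | n = 16 |
|---|---|---|
| 0 | 0 | 0 |
| 1 | 1/20 = 5 points | 1/16 = 6.3 points |
| 2 | 2/20 = 10 points | 2/16 = 12.5 points |
| 5 | 5/20 = 25 points | 5/16 = 31.3 points |
| 8 | 8/20 = 40 points | 8/16 = 50 points |

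Example, with a = 4 and p = 5 (both assumed). At n = 20, the record shows 16/20 = 80% without help, while 11/20 = 55% had none. At n = 16, the record shows 12/16 = 75%, while 7/16 = 43.8% had none.

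The difference cannot be negative. If partner help occurs, and forms without recorded help are read as independent, the error runs only towards greater apparent independence.

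**Step 3: which outcomes are exposed?**

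Self-efficacy, readiness and ACP discussions are exposed because their source is the patient survey. Advance directive completion, the primary ACP outcome in the SAP, is taken from the medical record (Table 5) and is not affected.

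**The case against.** The strongest reply is that nothing shows partners will help with surveys, and that the measure is coherent for a narrower purpose. Q2a asks whether outcomes can be collected, not whether patients can report alone. Staff help is a resource cost worth knowing before a pragmatic trial. Eligibility requires preserved functional independence, no dementia and demonstrated understanding for consent, which makes heavy partner completion less likely. The survey forms are not reproduced in the documents and may already ask who helped. All of this stands. It makes the concern conditional, but it does not supply the missing information: even if a form has such a field, neither analysis plan says it will be used.

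A reader might infer stronger claims that the documents do not support:

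- **That the intervention makes the partner the scribe for surveys.** Table 4 lists the role as a potential adaptation, for goal-setting and ACP decisions. It makes help with forms plausible and shows no more than that.
- **That partner-helped forms are scored as unassisted.** Neither document defines such a score or category, or a threshold for self-report. What is certain is only that no research-assistant help would be recorded.
- **That every survey is affected alike.** The 3-month survey is by telephone. A caller would ordinarily read the questions and record the answers. If that caller is a research assistant (not stated), the form would show staff help. What could still be missed there is a partner prompting or answering.
- **That time to complete is biased towards feasibility.** Partner help could lengthen or shorten it.
- **That the pilot gives a rate.** In Table 3, 9 of 17 participants with perceived impairment attended with a partner. That is attendance, not help with surveys.

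**Conclusion.** The gap is real and appears in both documents: a stated feasibility measure leaves out the one other helper whom the design recruits with every patient. As written, the plan cannot distinguish a partner-helped survey from independent self-report, so the ability to self-report could be overstated and some patient-survey scores could be unmarked proxy answers. Whether this happens, and how often, is not shown.

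The size is 5 points (n = 20) or 6.3 points (n = 16) for each patient helped only by the partner, and zero if there are none. It rests on two assumptions: that some partners help on forms with no staff help, and that absence of recorded help is read as independence. This is a worthwhile, inexpensive improvement to an item already collected. It does not demonstrate that the results will be biased.

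**What to change.** In both documents, replace the tracked item with: level of assistance by source (none, research assistant, study partner, both) and by type (read aloud, repeated, wrote the answer, suggested or gave the answer), recorded on each patient survey. On the 3-month call, also note whether the partner was present or prompted, because reading aloud and recording answers are part of a telephone survey and say little there about the patient's need for help.

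Add one sentence to each analysis plan saying that completeness and patient-reported scores will be described by these categories. At this sample size a descriptive table is enough. Patients and partners need not complete their forms apart for this to work.

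The cost is about one extra line per form and one small table. If the existing forms already carry the field, only the analysis sentence is needed.

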**(ENACT-aMCI**

**NCT Number: NCT03711396**

**Document Date: May 22, 2018**

## RESEARCH AND STATISTICAL ANALYSIS PLAN

This supplement will prioritize stakeholder input to adapt the ACP-GV intervention for aMCI and ADRD patient-study partner dyads, and identify mechanisms of action underlying person-centered approaches to support ACP-related decision making. This study will provide necessary feasibility data and experience conducting patient-centered ACP research among individuals affected by aMCI and ADRD to inform a future pragmatic clinical trial of ACP decision making strategies in aMCI/ADRD. **Figure 1** shows an overview of activities.

**Supplement Aim 1: Identify appropriate ACP-GV intervention modifications for individuals with aMCI or ADRD by convening a longitudinal group of affected patient-study partner stakeholders.**

**Study Design:** To design for patients and caregivers, promote intervention feasibility, and return findings to participants, we will convene five aMCI patients and their study partners for three focus group-style meetings over one year to suggest and review ACP-GV adaptations. In line with stakeholder engagement methods from the parent K76 study, we will solicit individual and group-level input to identify suggestions for adapting the ACP-GV intervention so that it is appropriate for individuals affected by aMCI/ADRD, has defined intervention components (i.e. ACP decision tools, facilitation techniques, structural design aspects), and focuses on clinically meaningful ACP outcomes. The Aim 1 activities will address the following questions:

Question 1a: What evidence-based ACP decision tools should be used in the adapted ACP-GV?

Question 1b: How should facilitation or other structural design aspects of the ACP-GV be adapted?

Question 1c: What are meaningful aMCI/ADRD patient and caregiver outcomes related to ACP in the context of the ACP-GV (e.g., patient readiness for ACP, caregiver preparedness, ACP documentation)?

**Study Setting and Participants:** Participants with suspected aMCI and their study partners will be recruited from [name] studies and open recruitment from the University of Colorado. We will specifically recruit both men and women, ages 65 and older, and purposefully invite individuals from diverse self-reported racial/ethnic backgrounds to maximize potential for generalizability.

Inclusion criteria for the diagnosis of aMCI will be based on the National Institute on Aging and Alzheimer's Association workgroup *clinical* criteria for MCI, but will depart from the core clinical criteria in that we will focus specifically on individuals with early memory impairment. The rationale for this decision is that our goal is to enrich our aMCI cohort for likely AD pathology and minimize the likelihood of a non-degenerative primary etiology. Study criteria will thus include the following clinical determinations: a) cognitive complaint that reflects a decline in cognition; b) objective neuropsychological impairment in one or more domains, including memory, using comprehensive criteria by Jak (i.e., cutoff of 1 SD below normative data on two memory tests); c) preservation of independence in functional activities; and d) not meeting criteria for a dementia. Exclusion criteria will be: major psychiatric disorder (e.g., schizophrenia, bipolar disorder, major depression within past two years); neurological or autoimmune conditions affecting cognition (e.g., Parkinson's disease, epilepsy, multiple sclerosis, head trauma with loss of consciousness > than 30 min; large vessel infarct); systemic

medical illnesses (e.g., cancer, renal failure); substance abuse or dependence (DSM-V criteria); and current depression (defined as Geriatric Depression Scale [GDS] score > 15).

To maximize recruitment of aMCI subjects, we will also institute the following plan: 1) In addition to the parent projects, we will recruit from the Memory Disorders Clinic, the University of Colorado Hospital, and Seniors Clinic, which have collectively evaluated more than 1,200 aMCI and ADRD patients in the past two years. 2) We will work with the Department of Neurology's recruitment specialist to streamline the recruitment pipeline. [name] projects utilize a multi-step approach to screen participants, including a 10-minute phone screen and an in-person visit to the Rocky Mountain Alzheimer's Disease Center. The phone screen addresses basic demographics and history, and also serves to identify/confirm a participant study partner. Potential participants who pass this screen undergo an in-person cognitive evaluation and a mood assessment. Participants with suspected aMCI will undergo an additional screening of memory using a list-learning task, story recall, and visual recall (i.e., Story Recall, Visual Reproduction). All potential participants are reviewed by [name] to ensure that inclusion criteria are met.

**Longitudinal Stakeholder Group Sessions:** The stakeholder group will meet three times, aligned with Aim 2 activities as follows: at the beginning of the study, after two cycles of the ACP-GV intervention, and after completion of four cycles of ACP-GV intervention rapid-prototyping process. To promote participation, a brief description of the ACP-GV intervention and key discussion questions will be mailed prior to each meeting. At each meeting, we will review the overall purpose of achieving robust stakeholder input and introduce the ACP-related decision making topics for discussion. The group will share ideas, engage in a discussion about the suggested adaptations, and personally use ACP decision tools to make recommendations for use. At all three meetings, participants will discuss person-centered support for ACP decision making in the context of cognitive impairment, including suggestions for evidence-based ACP decision tools, appropriate adaptations to the ACP-GV intervention, and meaningful outcomes for individuals affected by aMCI/ADRD over short-term (months) and longer term (years) periods. Potential outcomes include patient readiness for ACP, caregiver preparedness, and ACP documentation. At the end of each meeting, we will summarize the ideas for the participants, and we will incorporate input into the ACP-GV rapid-cycle prototyping process. The mid-point and final meetings will include detailed feedback and discussion of ACP-GV intervention experiences so that stakeholders can make new or updated suggestions to promote the feasibility of ACP decision making in the ACP-GV intervention. The final meeting will also function as a form of "member checking" to assure that we have reached consensus on the final ACP-GV adaptation, including ability for stakeholders to review and revise the on-line Advance Care Planning Group Visit Implementation Manual.

**Data Collection:** All groups and interviews will be conducted at a convenient location for participants. A qualitative research assistant will create detailed field notes. All sessions (~1.5 hours each) will be audiotaped and transcribed. After each meeting, [name], a qualitative research analyst, and I will de-brief and utilize iterative, inductive and deductive analytical strategies including field notes and memoing; qualitative content methods of analysis; consultative and reflexive team analysis of the meeting transcriptions to identify suggested ACP decision tools (**Q1a**), appropriate facilitator or structural design adaptations (**Q1b**), and meaningful patient and study partner/caregiver outcomes (**Q1c**). Detailed logs of analysis and interpretation, transcripts, and coding will be maintained to ensure transparency. ATLAS.ti will be used for data management.

**Qualitative Analysis:** Data analysis occurs longitudinally and begins at the time of the first focus group meeting as participants generate ideas and provide concrete suggestions for intervention adaptation. The words participants use, their beliefs, needs and preferences will be described. The qualitative research analyst and I will initially code individually and then meet to discuss codes, establish inter-code reliability, and create an initial code list. The code list will be revisited and revised with each subsequent focus group meeting. Text within and between codes will be compared to develop themes. We will use observer triangulation (using the interdisciplinary team), participant triangulation (comparing patient and study partner perspectives) and member checking (eliciting feedback while returning results at the final meeting) to increase validity.

